**10.7.10 Modified Nail Psoriasis Severity Index (mNAPSI)**

mNAPSI is the tool to assess each abnormality for each of a subject's fingernails. Three features or groups of features (pitting, onycholysis and oil-drop dyschromia, and crumbling) of each fingernail will be graded on a scale from 0 to 3. Four features (leukonychia, splinter hemorrhages, hyperkeratosis, and red spots in the lunula) will be graded as either present or absent for each fingernail. After a subject has assessed all of their nails consider all aspects of all of the subject's fingernails and place a mark on the visual analog scale giving a global assessment of their fingernails. For detailed instruction, please see protocol Appendix K. The overall mNAPSI is calculated as the sum of all the components for all of a subject's nails. In the case of missing data for any component of mNAPSI sum up all available component values and divide it by the total weight (if a score ranges 0 – 1, the weight is 1. If a score ranges 0 – 3, the weight is 3), then multiply by 130 (the upper range of the total score). If missing more than half of the total weight then the total score will be set as missing.

**10.7.11 European League Against Rheumatism (EULAR) Response Criteria**

EULAR response will be evaluated according to the following table:

DAS28 at endpoint	Improvement in DAS28 from baseline:		
	> 1.2	> 0.6 and ≤ 1.2	≤ 0.6
≤ 3.2	Good	Moderate	None
> 3.2 and ≤ 5.1	Moderate	Moderate	None
> 5.1	Moderate	None	None

EULAR response will be analyzed as a binary variable with Good being defined as response and Moderate & None being defined as non-response.

**10.7.12                    Minimal Disease Activity (MDA) in PsA****Table 11.                    Minimal Disease Activity (MDA) Criteria in Psoriatic Arthritis**

---

A patient is classified as in MDA when 5 of the following 7 criteria are met:

- TJC68  $\leq$  1
- SJC66  $\leq$  1
- PASI  $\leq$  1 or BSA  $\leq$  3
- Patient assessment of pain  $\leq$  15
- PtGA  $\leq$  20
- HAQ-S  $\leq$  0.5
- Tender entheseal points  $\leq$  1

---

Derivation rules for MDA follow the same logic as ACR. MDA response can be determined if at least 5 of the 7 criteria are met (responder), or if at least 3 of the 7 criteria are not met (non-responder). Selection of multiple MDA responses within one visit window follows the same rules as ACR.

**10.7.13                    Static Physician's Global Assessment (sPGA)**

This sPGA is a 5 point score ranging from 0 to 4, based on the physician's assessment of the average thickness, erythema, and scaling of all psoriatic lesions (Table 12).

The assessment is considered "static" which refers to the subjects disease state at the time of the assessments, without comparison to any of the subject's previous disease states, whether at Baseline or at a previous visit.

A lower score indicates less body coverage, with 0 being clear and 1 being almost clear.

The investigator (or qualified site personnel) scores the erythema, induration and scaling of all psoriatic lesions from 0 – 4 based on the following descriptors:

**Scoring**

A composite score is generated from the above data and the final sPGA is determined from this composite score as follows:

---

Clear	0 = 0 for all three
Almost clear	1 = mean $> 0, < 1.5$
Mild	2 = mean $\geq 1.5, < 2.5$
Moderate	3 = mean $\geq 2.5, < 3.5$
Severe	4 = mean $\geq 3.5$

**Table 12. sPGA Rating Scale for Overall Psoriatic Disease**

Score	Short description	Detailed description
0	clear	No signs of psoriasis. Post-inflammatory hyperpigmentation may be present.
1	almost clear	Normal to pink coloration; Just detectable (possible slight elevation above normal skin) No to minimal focal scaling
2	mild	Pink to light red coloration Mild thickening (slight but definite elevation, typically edges are indistinct or sloped) Predominantly fine scaling
3	moderate	Dull to bright red coloration Clearly distinguishable to moderate thickening Moderate scaling
4	severe	Bright to deep dark red coloration; Severe thickening with hard edges Severe coarse scaling covering almost all or all lesions

#### **10.7.14 Psoriatic Arthritis Response Criteria (PsARC) Response of Psoriasis**

A subject is defined as a PsARC responder if, and only if, they have an improvement in two of the following four factors (with at least one factor being a joint count) and no worsening in the remaining factors:

- Patient global assessment of disease activity (0 – 100 mm VAS scale, improvement defined as decrease of  $\geq 20$  mm)
- Physician global assessment of disease activity (0 – 100 mm VAS scale, improvement defined as decrease  $\geq 20$  mm)
- Tender 68-joint count (improvement defined as decrease of  $\geq 30\%$ )
- Swollen 66-joint count (improvement defined as decrease of  $\geq 30\%$ )

Derivation rules for PsARC follow the same logic as ACR.

#### **10.7.15           Leeds Dactylitis Index (LDI)**

The LDI measures the ratio of the circumference of the affected digit to the circumference of the digit on the opposite hand or foot. The ratio of circumference is multiplied by a tenderness score, using a modification of LDI which is a binary score (1 for tender, 0 for non-tender), using a minimum difference of 10% to define a dactylitic digit. When the difference is less than 10% the LDI for that digit is 0. If both sides are considered involved, or the circumference of the contralateral digit cannot be obtained, the number will be compared to data provided in the standard reference tables. The reference tables for standard digit circumference are listed in Appendix A1. This modification is referred to as LDI basic and will be applied in this study. The LDI requires a finger circumference gauge or a tape measure to measure digital circumference. Overall LDI for a patient will be calculated as the sum of their individual LDIs from the digits where the assessment was done. The LDI for a single digit will be calculated using the formula  $(A/B-1)*100*C$ , where A is the circumference of the affected digit, B is the circumference of the contralateral digit (or digit from the reference table if it is also affected), and C is the binary tenderness score for the digit.

##### Dactylitis Count:

The dactylitis count is the number of fingers and toes with dactylitis that are affected, tender, and with a minimum circumference difference of 10%, with a range of 0 – 20. If a site is not assessed assign it a value of "0."

Presence of Dactylitis:

If dactylitis is present with any finger or toe, the subject is counted as a subject with dactylitis.

**10.7.16                   Leeds Enthesitis Index (LEI)**

LEI is a validated enthesitis index that uses 6 sites for evaluation of enthesitis: lateral epicondyle humerus left and right, Achilles tendon insertion left and right and medial condyle femur left and right. The LEI demonstrated substantial to excellent agreement with other scores in the indication of psoriatic arthritis. The LEI score ranges from 0 to 6.

Enthesitis Count:

Tenderness on examination is recorded as either present (1) or absent (0) for each of the 6 sites (If a site is not assessed assign it a value of "0"), for an overall score range of 0 – 6.

Presence of Enthesitis Based on LEI:

If enthesitis is present with any of the 6 sites for LEI, the subject is counted as a subject with enthesitis based on LEI.

**10.7.17                   Enthesitis (SPARCC)**

The SPARCC Enthesitis index is an outcome measure for enthesitis in SpA created by the Spondyloarthritis Research Consortium of Canada. Sixteen sites are evaluated.

Tenderness at each site is quantified on a dichotomous basis: 0 means non-tender and 1 means tender. The SPARCC Enthesitis index is calculated by taking the sum of the scores from the 16 sites. If a site is not assessed assign it a value of "0." The SPARCC score ranges from 0 to 16.

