## 6.5 Missing Data Handling

All data will be summarized as observed, and thus a subject who does not have an evaluation on a scheduled visit will be excluded from the summary for that visit.

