### **Calculation Rules for ACR Criteria**

A subject will be classified as an ACR20 (ACR50, ACR70) responder, if the following conditions are met:

1.  $\geq 20\%$  ( $50\%$ ,  $70\%$ ) improvement from baseline in tender joint count (TJC)\* and
2.  $\geq 20\%$  ( $50\%$ ,  $70\%$ ) improvement from baseline in swollen joint count (SJC)\* and
3.  $\geq 20\%$  ( $50\%$ ,  $70\%$ ) improvement from baseline in at least 3 of the following 5:
  - Patient's assessment of pain
  - Patient's Global Assessment of Disease Activity for Arthritis (PtGA)
  - Physician's Global Assessment of Disease Activity for Arthritis (PhGA)
  - Patient's self-assessment of physical function (i.e., measured by Health Assessment Questionnaire (HAQ-DI score)
  - Acute-phase reactant value CRP

There are seven components to be evaluated to define an ACR response. Missing values for each component can occur due to missing assessment, a missed visit or due to dropout from the study. Depending on the pattern of the missing components, ACR responses may be or may not be determined using observed values only.

To maximize the utilization of observed information at certain visits and to be scientifically robust as possible, the principle to calculate ACR response is to minimize imputation whenever possible. "As Observed" ACR responses will be calculated

first based on a derived visit window instead of the nominal visit identifier collected from the CRF.

To calculate "as observed" ACR responses:

- Identify the observed component xx% improvement indicator (0/1/missing), 1 means achieving  $\geq$  xx% improvement from baseline and 0 means < xx% improvement from baseline (e.g., xx% representing 20%/50%/70%).
- ACRxx = 0 if TJC indicator = 0 OR SJC indicator = 0 OR at least 3 out of 5 components improvement indicators = 0;
- ACRxx = 1 if TJC indicator = 1 AND SJC indicator = 1 AND at least 3 out of 5 components improvement indicators = 1
- For all other cases, "as observed" ACRxx = missing since ACRxx cannot be determined.

The following table illustrates examples for as-observed ACR calculations.

Example	TJC 68	SJC 66	Component 1	Component 2	Component 3	Component 4	Component 5	ACR20- Response?
A	1	1	1	1	1	.	.	Yes
B	1	0	1	1	1	1	1	No
C	.	0	.	.	.	.	.	No
D	1	.	1	1	1	1	1	.
E	1	1	0	0	0	1	1	No
F	.	.	0	0	0	.	.	No
G	1	1	1	1	0	0	.	.

Legend: 1 =  $\geq$  20% improved compared to baseline; 0 = < 20% improved compared to baseline; " ." missing

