**Table 9. Anatomical Joints Assessed for Calculation of Tender and Swollen Joint Counts (TJC68 and SJC66)**

Temporomandibular	Sternoclavicular	Acromio-clavicular	Shoulder
Elbow	Wrist	Metacarpophalangeal I	Metacarpophalangeal II
Metacarpophalangeal III	Metacarpophalangeal IV	Metacarpophalangeal V	Interphalangeal Thumb Joint
Proximal Interphalangeal Joint II of the Hand	Proximal Interphalangeal Joint III of the Hand	Proximal Interphalangeal Joint IV of the Hand	Proximal Interphalangeal Joint V of the Hand
Distal Interphalangeal Joint II of the Hand	Distal Interphalangeal Joint III of the Hand	Distal Interphalangeal Joint IV of the Hand	Distal Interphalangeal Joint V of the Hand
Hip a	Knee	Ankle	Transverse Tarsus
Metatarsophalangeal I	Metatarsophalangeal II	Metatarsophalangeal III	Metatarsophalangeal IV
Metatarsophalangeal V	Interphalangeal Joint I of the Foot	Proximal Interphalangeal Joint II of the Foot	Proximal Interphalangeal Joint III of the Foot
Proximal Interphalangeal Joint IV of the Foot	Proximal Interphalangeal Joint V of the Foot		

a. Hip joints are not assessed for swelling.

At each study visit, a joint evaluator assessed whether a particular joint was "tender or painful" where presence of tenderness was scored as "1" and the absence of tenderness was scored as "0." The total tender joint count (TJC68), which is based on 68 joints, will be derived as the sum of all "1"s and proportional extrapolation will be used to compute joint counts for the joints that are replaced or not assessed. A similar method will be followed for the derivation of total swollen joint count (SJC66), which is based on 66 joints as the hip joints are excluded. Thus, the range for TJC68 will be 0 to 68 and 0 to 66 for SJC66. Joints with surgery (e.g., joint replacement) will not be assessed.

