#### **10.7.18 Functional Assessment of Chronic Illness Therapy-Fatigue (FACIT-Fatigue)**

The FACIT-Fatigue is a 13-item questionnaire that assesses self-reported fatigue and its impact upon daily activities and function.

The purpose of FACIT-Fatigue in this study is to assess the impact of fatigue on subjects with PsA.

Number of items: 13 items: I feel fatigued (-), I feel weak all over (-), I feel listless (washed out) (-), I feel tired (-), I have trouble starting things because I am tired (-), I have trouble finishing things because I am tired (-), I have energy (+), I am able to do my usual activities (+), I need to sleep during the day (-), I am too tired to eat (-), I need help doing my usual activities (-), I am frustrated by being too tired to do the things I want to do (-), I have to limit my social activity because I am tired (-).

Response options/scale: Answers are based on a 5-point Likert scale. Responses of "not at all," "a little," "somewhat," "quite a bit," and "very much" are available for each question, and correspond to scores of 0, 1, 2, 3, and 4, respectively (4 = not at all fatigued

to 0 = very much fatigued). The FACIT Fatigue Scale is ranged from 0 to 52 and the higher the score, the better the quality of life.

Score for each item is calculated by either subtracted from 4 or adding 0 depending on whether it is a reversal item or not. FACIT Fatigue Scale is then calculated by adding up all item scores, multiplied by 13 and divided by the number of items answered. It is essentially a prorated subscale if there are missing values for some items. If less than or equal to 50% of the items are answered (e.g., 6 out of 13), the proration is not acceptable and the scale will not be computed.

Recall period for items: 7 days.

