#### **10.7.19                    Bath Ankylosing Spondylitis Disease Activity Index (BASDAI)**

The BASDAI is composed of 6 questions investigating 5 domains (fatigue, spinal pain, joint pain/swelling, areas of localized tenderness, morning stiffness), with 1 item for each of the first four domains and 2 items for the last domain (morning stiffness). Each item is scored on a one through 10 scale. A lower score indicates less disease activity.

Scoring of the BASDAI is as follows:

1. Measure each item of the BASDAI in centimeters (out of a total of 10)
2. BASDAI Score =  $0.2 * (Question\ 1 + Question\ 2 + Question\ 3 + Question\ 4 + 0.5 * Question\ 5 + 0.5 * Question\ 6)$

The BASDAI Score ranges from 0 – 10. If one or more items are unanswered, take the average of the non-missing items. If there is more than one mark for an item, take the average.

Below are the 6 questions.

3. How would you describe the overall level of fatigue/tiredness you have experienced?
4. How would you describe the overall level of AS neck, back or hip pain you have had?
5. How would you describe the overall level of pain/swelling in joints other than neck, back or hips you have had?
6. How would you describe the overall level of discomfort you have had from any areas tender to touch or pressure?
7. How would you describe the overall level of morning stiffness you have had from the time you wake up?
8. How long does your morning stiffness last from the time you wake up?

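### LEI and SPARCC score an unexamined site as non-tender, so a partly assessed visit can be undercounted but never overcounted; low priority, but the MDA result should be shown with bounds

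*SAP*

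**What the plan says.** - **Enthesitis indices.** SAP 10.7.16 (LEI, 6 sites) and 10.7.17 (SPARCC, 16 sites) sum 0/1 tenderness scores. Both carry the rule "If a site is not assessed assign it a value of" zero. Neither prorates or requires a minimum number of examined sites.
- **Whole visits.** SAP 6.5 summarises data as observed: "a subject who does not have an evaluation on a scheduled visit will be excluded from the summary for that visit". The zero rule therefore matters only when some sites were examined and others were not.
- **Other multi-item scores.** For joint counts (10.7.2), "proportional extrapolation will be used to compute joint counts for the joints that are replaced or not assessed". The mNAPSI (10.7.10) is prorated with a cut-off: "If missing more than half of the total weight then the total score will be set as missing". FACIT-Fatigue (10.7.18) is prorated too, and when half or fewer of the items are answered "the proration is not acceptable and the scale will not be computed". For BASDAI (10.7.19), "If one or more items are unanswered, take the average of the non-missing items". The dactylitis count (10.7.15) uses the same zero rule as LEI and SPARCC.
- **MDA.** SAP 10.7.12 makes a subject a responder when at least 5 of 7 criteria are met and a non-responder when at least 3 are not met. One criterion is at most 1 tender entheseal point; the index that supplies it is not named. The derivation is to follow the ACR logic of 10.7.1, where an unresolved result is "missing since ACRxx cannot be determined".
- **Recording.** Protocol Appendix E gives joints a separate code for not assessed. Appendices I and J define only present and absent for entheses.

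**The concern.** An unexamined enthesis is entered as a healthy one. Joint counts, which sit in the same MDA composite, are treated the opposite way: 1 tender of 67 examined joints extrapolates to 68/67 = 1.01, which without rounding fails a cut of 1. For the entheseal criterion, zero-filling also removes the undetermined outcome that the ACR logic would allow. What is at stake is an MDA criterion that can be wrong in one direction only, in a single-arm study with no comparator to share the error, and changes in LEI and SPARCC that are distorted in a direction depending on when sites were missed.

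**Working it through.** The plan states no figure for this point, so there is none to reproduce. Inputs are the site numbers (6 and 16), the cut of at most 1, and the 5-of-7 rule, all from the SAP. Shares of unexamined sites and tenderness probabilities are assumptions.

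**1. Direction of the count.** Let s be the tender sites among those examined and u the tender sites among those not examined. The SAP records s; the complete count is s + u, so s ≤ s + u always. Full enumeration of partly assessed visits (70 combinations for 6 sites, 935 for 16) found no exception. The recorded count was strictly lower in 50 and 800 of them and equal in the rest; these are unweighted tallies, not probabilities.

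**2. MDA criterion falsely met.** Take 2 truly tender sites and k unexamined at random. The recorded count is at most 1 unless both tender sites were examined.
- LEI, 1 − C(4,k)/C(6,k): k = 1, 1 − 4/6 = 0.33; k = 2, 1 − 6/15 = 0.60; k = 3, 1 − 4/20 = 0.80.
- SPARCC, 1 − C(14,k)/C(16,k): k = 1, 1 − 14/16 = 0.13; k = 2, 1 − 91/120 = 0.24; k = 4, 1 − 1001/1820 = 0.45.

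**3. When this changes MDA.** The other six criteria can be met / not met / missing in C(8,2) = 28 patterns. A false 'met' changes the result in 7:
- 4/2/0: non-responder becomes responder.
- 4/1/1 and 4/0/2: missing becomes responder.
- 3/2/1, 2/2/2, 1/2/3 and 0/2/4: non-responder becomes missing and leaves the observed-case denominator.

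Each raises the observed-case rate or leaves it unchanged.

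**4. Illustration for the MDA rate, LEI as index.** Rate effect = share of visits partly assessed × share of those with exactly 4 of the other six met and a true count of 2 × P(falsely met).
- Low: 0.01 × 0.05 × 0.333 = 0.02 percentage points.
- High: 0.10 × 0.20 × 0.80 = 1.6 percentage points.

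This is not a bound. A true LEI count of 3 is also falsely met, with probability 3/15 = 0.20 (k = 2) or 10/20 = 0.50 (k = 3), and is left out.

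**5. Change from baseline.** The expected zero-filled score is true × examined/total; the expected prorated score equals the true score.

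| Expected change | Truth | Missed later only | Missed at baseline only | Missed at both |
|---|---|---|---|---|
| SPARCC 8 to 4, 4 of 16 unexamined, zero-filled | −4 | 8 to 3 = −5 | 6 to 4 = −2 | 6 to 3 = −3 |
| LEI 3 to 1, 1 of 6 unexamined, zero-filled | −2 | −2.17 | −1.50 | −1.67 |
| Prorated at both times | truth | truth | truth | truth |

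Mixing rules can be worse. With SPARCC sites missed at both times, a zero-filled baseline and a prorated later score give 6 to 4 = −2, against −3 under the present rule.

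**6. Candidate repairs for MDA.** Applying the cut to a prorated score fails every partly assessed visit with one observed tender site (1 of 5 examined LEI sites gives 1.2). The alternative is a determinability rule: met if tender plus unexamined sites total at most 1; not met if 2 or more examined sites are tender; otherwise undetermined and dropped. Assume independent sites with tenderness probability p, so that P(at most 1 of n) = (1 − p)^n + np(1 − p)^(n−1). Where this criterion decides MDA, P(met) is:

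| Case | Complete data | Zero-fill | Determinability, among determined |
|---|---|---|---|
| LEI 4 of 6 examined, p = 0.1 | 0.886 | 0.948 | 0 |
| LEI 5 of 6, p = 0.1 | 0.886 | 0.919 | 0.879 |
| LEI 5 of 6, p = 0.2 | 0.655 | 0.737 | 0.555 |
| SPARCC 15 of 16, p = 0.1 | 0.515 | 0.549 | 0.313 |

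Dropping undetermined items biases the rate downward, often by more than zero-filling biases it upward. Zero-fill is exactly the result of counting every undetermined item as met, so it is one end of a range and can be reported as such.

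**The case against.** The strongest case for leaving the rule alone has four parts.

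- **Cases may not exist.** The protocol defines only present and absent for entheses, and the eCRF is not in the documents. This stands, and is a reason for low priority and for counting unexamined sites first.
- **The rule is a prespecified convention, not an oddity.** It is shared with the dactylitis count, and joint counts and BASDAI also set no minimum. A reader might infer that LEI and SPARCC are the only lax scores in the SAP; they are not. What remains is the contrast with the prorated scores, and the link to MDA, in which dactylitis plays no part.
- **An obvious repair can do harm.** A reader might infer that undetermined MDA items should be set to missing in the headline rate. Step 6 shows why not: with 2 or more sites unexamined, such a rule can never return met, so every true 'met' is dropped while some true 'not met' are kept. This objection stands and shapes the fix.
- **Baseline comes from another sponsor's study.** Nothing in the documents shows that site-level data from Study 1311.5 are available, and prorating only the later visits can worsen the change score. This also stands.

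**Conclusion.** The point holds in a limited form. At a partly assessed visit the LEI or SPARCC count can be lowered or left unchanged, never raised. If either index supplies the MDA criterion, which is a reasonable inference but not stated, the error there runs only toward met. The probabilities in step 2 rest on sites being missed at random and on a true count of 2.

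Three stronger readings are not supported:
- That the rule inflates reported improvement in enthesitis. Sites missed at baseline understate improvement and sites missed later overstate it.
- That missed visits are counted as healthy. SAP 6.5 excludes them.
- That the MDA rate is overstated by up to 1.6 points. That figure illustrates assumed inputs and is neither an estimate nor a limit.

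The documents give no rate of unexamined sites, and SAP 10.1 and 10.4 make these descriptive, untested further endpoints in a study whose primary objective is safety. Priority is low; the case for acting is that the direction for MDA is known and the repair is cheap.

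**What to change.** 1. **Change in LEI and SPARCC (SAP 10.7.16, 10.7.17).** Use score = tender sites / examined sites × total sites, set to missing if more than half the sites are unexamined (the mNAPSI cut-off). Do this only where the same rule can be applied to the Study 1311.5 baseline and to later visits. If site-level baseline data are not available, keep one rule at both times; do not set a zero-filled baseline against prorated later scores.
2. **MDA (SAP 10.7.12).** Name the index. Do not apply the cut of 1 to a prorated score, and do not replace the headline with a rate that drops undetermined items. Keep the present result, label it the upper bound (undetermined entheseal items counted as met), and report beside it the rate with those items counted as not met. An item is undetermined when at most 1 examined site is tender but tender plus unexamined sites total 2 or more.
3. **Reporting.** Tabulate the number of unexamined sites by visit, including baseline. This requires the eCRF to hold not assessed separately from zero, which should be confirmed.

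**Cost.** A few sentences, slight extra programming, a few more missing change scores, and two derivations of one index. The upper bound is what the current rule already produces. The bounds may be wide where sites are missed: with 1 LEI site unexamined, the item is undetermined with probability 0, 0.83 or 0.33 for a true count of 0, 1 or 2, and with 2 or more unexamined a true count of 0 or 1 is always undetermined.
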